6.19.1. Endpoints

Efficacy analyses include clinical remission, clinical response, mucosal healing, and changes in Mayo score.

Endoscopy images will be obtained during each endoscopy and will be sent to Robarts Clinical Trials for central reading and determination of the Mayo endoscopy score. The result of the central reading of the endoscopy will be used to ensure patient eligibility prior to randomization and to calculate the Mayo score at the times indicated in the schedule of events. The Mayo score used for clinical endpoints in the study will utilize the Mayo endoscopy score derived from the central reader. Sensitivity analyses of clinical endpoints using the Mayo score derived from the investigator interpretation will be performed.

6.19.2. Primary Efficacy Analysis

The primary analysis will be carried out when all patients have completed (or would have been eligible to complete) the IP of the study (Week 8).

The primary endpoint of proportion of patients in clinical remission at Week 8 will be analyzed using the Cochran-Mantel-Haenszel (CMH) test, stratified by prior anti-TNF therapy experience (yes or no). The primary analysis will use the data from the 1 mg dose and placebo groups and compare the remission rates in these two groups using a two-sided test at the 0.05 level of significance. The second comparison for the primary endpoint will be the comparison of remission rates between the 0.5 mg group and the placebo group. The CMH p-value and the relative risk along with its 95% CI will be provided for each treatment group. In addition, the treatment difference and associated 95% CI will also be provided.

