13.8.3. Key Secondary Analyses

If the primary efficacy analysis is statistically significant ($p < 0.05$), then additional confirmatory tests using the ITT population will be performed in the following prespecified order:

- Proportion of patients in clinical remission at Week 8: 0.5 mg dose versus placebo
- Proportion of patients in clinical response at Week 8: 1 mg dose versus placebo
- Proportion of patients in clinical response at Week 8: 0.5 mg dose versus placebo
- Change in Mayo score from baseline at Week 8: 1 mg dose versus placebo
- Change in Mayo score from baseline at Week 8: 0.5 mg dose versus placebo
- Proportion of patients with mucosal healing at Week 8: 1 mg dose versus placebo
- Proportion of patients with mucosal healing at Week 8: 0.5 mg dose versus placebo
- Proportion of patients in clinical remission at Week 32: 1 mg dose versus placebo
- Proportion of patients in clinical remission at Week 32: 0.5 mg dose versus placebo
- Proportion of patients in clinical response at Week 32: 1 mg dose versus placebo
- Proportion of patients in clinical response at Week 32: 0.5 mg dose versus placebo
- Change in Mayo score from baseline at Week 32: 1 mg dose versus placebo
- Change in Mayo score from baseline at Week 32: 0.5 mg dose versus placebo
- Proportion of patients with mucosal healing at Week 32: 1 mg dose versus placebo
- Proportion of patients with mucosal healing at Week 32: 0.5 mg dose versus placebo

Provided that all previously specified tests are statistically significant ($p < 0.05$), each of these comparisons will be assessed using a two-sided test at the $\alpha = 0.05$ level of significance.

However, if a comparison is not statistically significant, then all subsequent comparisons will be considered exploratory.

Secondary endpoints that are defined as proportions will be analyzed using the same type of methodology as described for the primary analysis. Analyses of all proportion endpoints using the CMH test will be completed using the data from the two groups being compared. Quantitative secondary endpoints will be analyzed using analysis of covariance (ANCOVA) models with effects for treatment group (three levels) and prior anti-TNF therapy experience, and with the baseline value of the corresponding endpoint included as a covariate. All secondary analyses will be carried out using two-sided test at the 5% level of significance.

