3.1.3. Exploratory Objectives

3.2. Endpoints

3.2.1. Efficacy Endpoints

Primary Efficacy Endpoint:

[figure not shown]
• The primary endpoint is the proportion of patients in clinical remission at Week 8, defined as a Mayo score of ≤ 2 points and with no individual subscore of > 1 point

Key Secondary Efficacy Endpoints (rank ordered):

- Proportion of patients with a clinical response at Week 8, defined as a reduction from baseline in Mayo score of ≥ 3 points and ≥ 30%, and a decrease from baseline in the rectal bleeding subscore of ≥ 1 point or an absolute rectal bleeding subscore of ≤ 1 point
- Change from baseline in Mayo score at Week 8
- Proportion of patients with mucosal healing at Week 8, defined by an endoscopy subscore of ≤ 1
 point

Other Secondary Efficacy Endpoints:

- Proportion of patients in clinical remission at Week 32 defined as Mayo score of ≤ 2 points with no individual subscore of > 1 point
- Proportion of patients with a clinical response at Week 32, defined as a reduction from baseline in Mayo score of ≥ 3 points and ≥ 30%, and a decrease from baseline in the rectal bleeding subscore of ≥ 1 point or an absolute rectal bleeding subscore of ≤ 1 point
- Proportion of patients with mucosal healing at Week 32, defined by an endoscopy subscore of ≤ 1 point

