6.10. Final Analyses and Reporting

The primary analysis will be carried out when all patients have completed (or would have been eligible to complete) the IP of the study. The randomized treatment groups will be unblinded for both the IP and MP for the primary analysis. At the time of the primary analysis, the database will be locked for all visits through Week 8 and the available Mayo score data will be cleaned for all visits beyond Week 8. Data will continue to accrue for the MP and OLP visits. For this primary analysis, the safety analyses will be summarized for the IP only.

Final database lock will occur when all patients have completed the study and all data during the assessment periods has been monitored. In addition, no database may be locked, randomization code unblinded, or analyses completed (other than analyses for the DMC) until this SAP has been approved. All analyses outlined in the protocol and in this SAP (other than analyses conducted for the DMC) will be carried out after:

- The SAP has been approved
- All analysis populations are determined

Further exploratory analyses not necessarily identified in this SAP may be performed to support the CSR. Any post-hoc or unplanned analyses performed and not identified in this SAP will be clearly identified in the CSR.

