6.19.3. Secondary Efficacy Analyses

If the primary efficacy analysis is statistically significant (p < 0.05), then additional confirmatory tests using the ITT population will be performed in the following prespecified order:

- Proportion of patients in clinical response at Week 8: 1 mg dose versus placebo
- Proportion of patients in clinical response at Week 8: 0.5 mg dose versus placebo
- Change in Mayo score from baseline at Week 8: 1 mg dose versus placebo
- Change in Mayo score from baseline at Week 8: 0.5 mg dose versus placebo
- Proportion of patients with mucosal healing at Week 8: 1 mg dose versus placebo
- Proportion of patients with mucosal healing at Week 8: 0.5 mg dose versus placebo

Provided that all previously specified tests are statistically significant (p < 0.05), each of these comparisons will be assessed using a two-sided test at the 0.05 level of significance. However, if a comparison is not statistically significant, then all subsequent comparisons will be considered exploratory.

Secondary endpoints that are defined as proportions will be analyzed using the same type of methodology as described for the primary analysis. Analyses of all proportion endpoints using the CMH test will be completed using the data from the two groups being compared. Quantitative secondary endpoints such as change in Mayo score will be analyzed using analysis of covariance (ANCOVA) models with effects for treatment group and prior anti-TNF therapy experience, and with the baseline value of the corresponding endpoint included as a covariate. All secondary analyses will be carried out using two-sided test at the 5% level of significance.

Actual and change from baseline in Mayo scores over time will be plotted.

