6.19.6. Other Efficacy Analyses

6.19.6.1. Mayo Score at Week **32**

The analyses will be performed for all available Week32 data at the time of database lock as described in Section 6.10.

- Proportion of patients in clinical remission at Week 32
- Proportion of patients in clinical response at Week 32
- Change in Mayo score from baseline at Week 32
- Proportion of patients with mucosal healing at Week 32

The endpoints that are defined as proportions will be analyzed using the same type of methodology as described for the primary analysis. Analyses of all proportion endpoints using the CMH test will be completed using the data from the two groups being compared. Quantitative secondary endpoints such as change in Mayo score will be analyzed using ANCOVA models with effects for treatment group and prior anti-TNF therapy experience, and with the baseline value of the corresponding endpoint included as a covariate. All analyses will be carried out using two-sided test at the 5% level of significance.

Actual and change from baseline in partial Mayo scores over time will be plotted.

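### The protocol and SAP do not give one confirmatory testing sequence: the SAP leaves the gate for 0.5 mg Week 8 remission unclear, and it places outside the chain the Week 32 tests that the protocol gates

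*SAP*

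**What the plan says.** **Week 8.** Both documents make 1 mg versus placebo on Week 8 remission the primary test (CMH, two-sided 0.05). If it is significant, protocol 13.8.3 continues with a fixed sequence whose first entry is "Proportion of patients in clinical remission at Week 8: 0.5 mg dose versus placebo"; each later test counts as confirmatory only if every earlier one was significant. SAP 6.19.2 instead states: "The second comparison for the primary endpoint will be the comparison of remission rates between the 0.5 mg group and the placebo group". It gives no condition for that comparison. SAP 6.19.3 then says that, if the primary efficacy analysis is significant, "additional confirmatory tests using the ITT population will be performed in the following prespecified order". Its list starts with 1 mg clinical response and does not contain 0.5 mg remission. The same section adds the condition "Provided that all previously specified tests are statistically significant".

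**Week 32.** The protocol's sequence continues into Week 32, beginning with "Proportion of patients in clinical remission at Week 32: 1 mg dose versus placebo". SAP 3.2.1 ranks only Week 8 endpoints as key secondary and puts Week 32 under "Other Secondary Efficacy Endpoints". SAP 6.19.6.1 tests the Week 32 endpoints at a two-sided 5% level with no gate and says: "The analyses will be performed for all available Week32 data at the time of database lock as described in Section 6.10".

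**Recorded departures.** SAP Section 8 lists two departures from the protocol, histologic remission and plasma protein biomarkers. It does not mention the testing sequence.

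**The concern.** A fixed sequence controls error only if the order and the gates are settled before unblinding. Here two questions have no single answer in the current texts.

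- If 1 mg remission is significant and 0.5 mg remission is not, is 1 mg clinical response still a confirmatory test? The protocol says no. A literal reading of the SAP list says yes.
- Is a significant Week 32 result confirmatory? The protocol says yes, if everything before it succeeded. The SAP places it outside the confirmatory list.

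At stake are the status of the secondary claims and, on some readings of the SAP, familywise error across the Week 8 tests.

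**Working it through.** **1. The plan's own figure.** Protocol 13.2 and SAP 6.5 give 80% power with 60 per group, placebo 10%, active 31%, two-sided 0.05. With the pooled normal approximation:

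- mean rate = (0.10 + 0.31)/2 = 0.205
- null SE = √(2 × 0.205 × 0.795/60) = 0.0737
- alternative SE = √((0.10 × 0.90 + 0.31 × 0.69)/60) = 0.0712
- power = Φ((0.21 − 1.96 × 0.0737)/0.0712) = 82.1%

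The normal approximation to the stratified CMH test (two equal strata, 30 per arm in each) gives 81.7%. The stated power is reproduced. It concerns one pairwise comparison and does not depend on the sequence.

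**2. Counting the confirmatory tests after the primary.**

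| | Protocol 13.8.3 | SAP 6.19.3 list |
|---|---|---|
| 0.5 mg Week 8 remission | 1 | 0 |
| Week 8 response, Mayo change, mucosal healing (two doses each) | 6 | 6 |
| Week 32 remission, response, Mayo change, mucosal healing (two doses each) | 8 | 0 |
| Total | 15 | 6 |

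The difference is 15 − 6 = 9: the 0.5 mg Week 8 remission test and the eight Week 32 tests.

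**3. Week 8 familywise error under each reading of the SAP.** Two doses share one placebo arm with 1:1:1 allocation, so under the null the two dose comparisons on one endpoint correlate at 0.5. The documents give no correlation between endpoints; 0 to 0.7 is an assumed range. Results are from numerical integration and a 1,000,000-replicate simulation of the eight Week 8 tests (the primary plus seven).

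- *(a) Serial, as in the protocol.* 0.5 mg remission is step 2 and gates the rest. Error is at most 0.05 (simulated 0.050 under the global null).
- *(b) Ungated at 0.05.* Under the global null a false claim arises if either remission test rejects: 1 − P(|Z1| ≤ 1.96 and |Z2| ≤ 1.96) at correlation 0.5 = 0.091.
- *(c) Gated on 1 mg remission, but not a gate for the list.* Under the global null, 0.050. If 1 mg remission is truly effective, and 0.5 mg remission and the list hypotheses are null, then 0.5 mg remission and 1 mg response are each tested at 0.05. For independent tests the error is 1 − 0.95² = 0.0975. Simulation gives 0.098 at between-endpoint correlation 0, falling to 0.095 at 0.7. Reading (b) gives the same values in this setting.

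In a less extreme case, with 1 mg at 80% power on every endpoint and 0.5 mg null throughout, simulated error is about 0.033 under (a), 0.071 to 0.076 under (b) and 0.055 to 0.060 under (c).

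**4. Which Week 32 data.** SAP 6.10 describes two locks: one for the primary analysis, covering visits through Week 8, and a final one when all patients have completed the study. For the first, the available Mayo data beyond Week 8 are to be cleaned, and "The randomized treatment groups will be unblinded for both the IP and MP for the primary analysis". Read with the reference in SAP 6.19.6.1 to all available Week 32 data, this most likely means an analysis of partial Week 32 data at the primary-analysis lock.

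**5. Does moving Week 32 affect Week 8?** No. The Week 32 tests come last in the protocol's chain, so removing them leaves every earlier gate unchanged.

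**The case against.** The strongest reply on Week 8 is that the serial reading is the natural one. SAP 6.19.2 covers the primary endpoint and ranks the 0.5 mg comparison second. SAP 6.19.3 covers secondary endpoints, so a primary-endpoint comparison could be absent from its list simply because of how the SAP is organised. The condition "Provided that all previously specified tests are statistically significant" can be taken to include it, and protocol 13.3 says the SAP expands on the protocol. This stands far enough that a reader should not infer that the SAP has dropped the gate or that error is certainly inflated. It does not remove the problem, because SAP 6.19.3 also opens its list on the primary efficacy analysis alone, which SAP 6.19.2 defines as 1 mg versus placebo.

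On Week 32, the reply is that the SAP is internally clear that these tests are not confirmatory, and that the main SAP may follow an earlier protocol version: it carries a different sponsor name and a 30-day rather than a 90-day safety follow-up. Both points are fair. They may explain the difference between the current texts, but they do not resolve it.

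Four stronger inferences are not supported:

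- *That nobody can tell which lock applies.* SAP 6.10 and 6.19.6.1 together point to the primary-analysis lock, although neither says so outright.
- *That the chance of 1 mg remission succeeding while 0.5 mg fails measures the harm.* With 1 mg at 31% and placebo at 10%, it is 10% to 71% for assumed 0.5 mg rates of 31% down to 15%. That is a design probability, not an error rate, and it matters only on the literal reading.
- *That about 31% of randomized patients (168/548 days, 55 of 180) would lack Week 32 data.* This assumes uniform accrual over 18 months and counts Week 8 non-responders, who never enter the Maintenance Period. With an assumed 30% to 60% response, about 17 to 33 patients would be pending. The 18 months also come from protocol 9.4, whose 32-month total does not fit the synopsis dates of October 2012 to December 2019.
- *That this point establishes a blinding failure.* Who sees treatment codes at the Week 8 lock is a separate issue.

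**Conclusion.** The point holds as a need to reconcile the current documents.

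**Week 8** is an ambiguity. On the serial reading the documents agree and familywise error is 0.05. If 0.5 mg remission is ungated, error is about 0.09 under the global null. If it is gated on 1 mg but does not gate the list, error can reach about 0.098. The global-null figure rests on the shared placebo arm. The upper figure also assumes a truly effective 1 mg dose on remission, null hypotheses at the next steps, and near-independent endpoints.

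**Week 32** is a direct difference: eight gated confirmatory tests in the protocol, and ungated 5% tests outside the confirmatory list in the SAP, not recorded in SAP Section 8. The consequence is the status of the Week 32 results. Partial data at the primary-analysis lock would not be a sound basis for the protocol's confirmatory tests.

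The 1 mg primary test and the stated power are untouched. This should be fixed, but it does not threaten the main result.

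**What to change.** **Week 8.** State in SAP 6.19.2 and 6.19.3 that 0.5 mg Week 8 remission is step 2, tested at two-sided 0.05 only if 1 mg remission is significant, and that the response, Mayo change and mucosal healing steps follow only if step 2 is significant. This adopts the protocol's existing order and costs a sentence or two of SAP wording.

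**Week 32.** Choose one:

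- label the Week 32 p-values nominal in both documents, which needs a protocol amendment; or
- keep the protocol's gated Week 32 steps and test them once, on complete data, at a named lock after all patients have reached Week 32. This adds a lock to SAP 6.10 and delays Week 32 claims until then.

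Record any remaining departure from the protocol in SAP Section 8. If treatment codes have already been opened, report confirmatory status under each sequence rather than choosing one after seeing the results. The price is that some secondary results may have to be called exploratory.

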6.19.3. Secondary Efficacy Analyses

If the primary efficacy analysis is statistically significant (p < 0.05), then additional confirmatory tests using the ITT population will be performed in the following prespecified order:

- Proportion of patients in clinical response at Week 8: 1 mg dose versus placebo
- Proportion of patients in clinical response at Week 8: 0.5 mg dose versus placebo
- Change in Mayo score from baseline at Week 8: 1 mg dose versus placebo
- Change in Mayo score from baseline at Week 8: 0.5 mg dose versus placebo
- Proportion of patients with mucosal healing at Week 8: 1 mg dose versus placebo
- Proportion of patients with mucosal healing at Week 8: 0.5 mg dose versus placebo

Provided that all previously specified tests are statistically significant (p < 0.05), each of these comparisons will be assessed using a two-sided test at the 0.05 level of significance. However, if a comparison is not statistically significant, then all subsequent comparisons will be considered exploratory.

Secondary endpoints that are defined as proportions will be analyzed using the same type of methodology as described for the primary analysis. Analyses of all proportion endpoints using the CMH test will be completed using the data from the two groups being compared. Quantitative secondary endpoints such as change in Mayo score will be analyzed using analysis of covariance (ANCOVA) models with effects for treatment group and prior anti-TNF therapy experience, and with the baseline value of the corresponding endpoint included as a covariate. All secondary analyses will be carried out using two-sided test at the 5% level of significance.

Actual and change from baseline in Mayo scores over time will be plotted.

6.19.4. Exploratory Efficacy Analyses

6.19.5. Sensitivity Analyses

Sensitivity analyses will be carried out to assess homogeneity of the results for the primary and key secondary endpoints across geographical regions. In these analyses, geographic region will be categorized as North America, Europe, and Asia Pacific. For proportion endpoints, these analyses will be carried out using logistic regression models including effects for treatment group, prior anti-TNF therapy experience, geographic region, and the interaction between treatment group and geographic region. If interactions cannot be excluded, results will be summarized by geographic region. Similarly, quantitative endpoints will be analyzed using ANCOVA models as described previously, with the addition of effects for geographic region and the interaction between treatment group and geographic region.

Sensitivity analyses of the primary and key secondary endpoints will be carried out to investigate the impact of missing data on the efficacy conclusions. All sensitivity analyses will be conducted in the ITT population. The primary and secondary efficacy analyses will be repeated using the following missing data methods:

- Analyses using LOCF (except change in Mayo score)
- Analyses of observed cases (i.e., using only observed data, with no imputation for missing data)
- Multiple imputation model-based methods

Finally, each of the primary and key secondary endpoint analyses will be repeated using clinical endpoints derived from the Mayo score using the investigator endoscopy interpretation.

6.19.6. Other Efficacy Analyses

6.19.6.1. Mayo Score at Week **32**

The analyses will be performed for all available Week32 data at the time of database lock as described in Section 6.10.

- Proportion of patients in clinical remission at Week 32
- Proportion of patients in clinical response at Week 32
- Change in Mayo score from baseline at Week 32
- Proportion of patients with mucosal healing at Week 32

The endpoints that are defined as proportions will be analyzed using the same type of methodology as described for the primary analysis. Analyses of all proportion endpoints using the CMH test will be completed using the data from the two groups being compared. Quantitative secondary endpoints such as change in Mayo score will be analyzed using ANCOVA models with effects for treatment group and prior anti-TNF therapy experience, and with the baseline value of the corresponding endpoint included as a covariate. All analyses will be carried out using two-sided test at the 5% level of significance.

Actual and change from baseline in partial Mayo scores over time will be plotted.

